- Total bilirubin $\leq 2.0 \times \text{ULN}$.

- 3.1.6 Female patients capable of reproduction and male patients who have partners capable of reproduction must agree to use an effective contraceptive method during the course of the study and for -1 month following the completion of their last treatment. Acceptable methods of contraception are condoms with contraceptive foam, oral, implantable or injectable contraceptives, contraceptive patch, intrauterine device, diaphragm with spermicidal gel, or a sexual partner who is surgically sterilized or post-menopausal.
- 3.1.7 Female of childbearing potential must have a negative serum β -Hcg pregnancy test result within 3 days of first study dose. Female patients who are surgically sterilized or who are > 45 years old and have not experienced menses for > 2 years may have β -Hcg pregnancy test waived.
- 3.1.8 Patients with a history of hepatitis B (surface antigen or core antibody positive and PCR positive) must take lamivudine or equivalent drug during study therapy and for one year after completion of all therapy. Patients on IVIG who are core antibody positive but PCR negative are not mandated to take prophylaxis.
- 3.1.9 Ability to understand and the willingness to sign a written informed consent document.
- 3.1.10 Patients enrolled into cohort 3 must have high-risk disease with higher risk of relapse on ibrutinib. This includes patients with complex karyotype (3 or more cytogenetic abnormalities) or high/very high risk by CLL-IPI (<https://www.mdcalc.com/international-prognostic-index-chronic-lymphocytic-leukemia-ctl-ipi>)

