4. REGISTRATION PROCEDURES

For subsite patients, sites must send the signed consent form, documentation of the consent process, and the Screening Form (refer to Supplemental Forms Document) within 2 business days of initial consent.

Patients will be registered after meeting all entry requirements, clearance by the Protocol Coordinator, and signing of the informed consent.

OSU patients will be registered by the OSU research coordinator, as per their standard practice.

Subsite patients will have eligibility verified and will be entered on study centrally at the Ohio State University by the Multi-Center Trial Program (MCTP). All subsites must email the MCTP to verify slot availability prior to consenting patients. The required forms, including Eligibility Criteria Checklist and Registration Form, can be found in the Supplemental Forms Document.

To register a subsite patient, the following documents must be completed by the subsite research team and faxed or securely e-mailed to the MCTP:

- Copy of all baseline tests required per the protocol calendar. Tests must be within the specified window.
- Signed Patient Consent Form
- Signed Patient HIPAA Authorization Form
- Consent Documentation Note

- Completed & Signed Eligibility Checklist (refer to Supplemental Forms Document)
- Registration Form (refer to Supplemental Forms Document)
- Source documents verifying every inclusion & exclusion criteria
 - Note: every inclusion and exclusion criteria must be documented in the patient's medical record (emails or other notes outside the medical record will not be considered source documentation)

Upon receipt of registration documents, the MCTP will send an email confirmation of receipt. If confirmation of receipt is not received within 1 hour of submission, please call or page the MCTP.

Upon receipt of all required registration documents and upon verification the subsite patient meets all eligibility criteria, the MCTP will:

- Register the patient on the study
- Fax and/or e-mail to the subsite the completed Registration Form with the assigned study ID as confirmation of patient registration

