5.4.1.1 Permitted Concomitant Medications

5.5 Prevention of Pregnancy

Female patients of child-bearing potential must agree to use dual methods of contraception and have a negative serum pregnancy test at screening, and male patients must use an effective barrier method of contraception if sexually active with a female of child-bearing potential. Acceptable methods of contraception are condoms with contraceptive foam, oral, implantable or injectable contraceptives, contraceptive patch, intrauterine device, diaphragm with spermicidal gel, or a sexual partner who is surgically sterilized or post-menopausal. For both male and female patients, effective methods of contraception must be used throughout the study and for one month following the last dose.

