PET/CT or CT scans	X					X ^m		X ⁿ	X ^o	X	X ^h
Bone marrow biopsy and aspirate	X ^p							X ^q	X ^q		X ^q
Histologic review	X ^r										
Correlative studies	See Correlative Study Calendar										

- Initial medical history should include: baseline symptoms; a detailed history of prior cancer therapies including start and stop dates, disease progression during or after therapy, as well as discontinuations due to intolerability or any other serious illness; family and social history; calculation of Rai Stage (for CLL patients), MIPI (for MCL patients), or IPI (NHL patients other than MCL; see Appendix C).
- Progress notes should include: new symptoms or adverse events, ECOG performance status (Appendix A), documentation of physical exam, status of disease.
- Ophthalmologic exam: required at screening, if clinically indicated during study, and at final visit. Prior to dilation: best corrected visual acuity, visual field examination via automated perimetry, tonometry, and color vision test. Dilated funduscopy and slit lamp exam including anterior segment photos to document lens clarity.
- For ECOG performance status, see Appendix A
- Prothrombin time, international normalization ratio, and activated partial thromboplastin time
- Sodium, potassium, bicarbonate, BUN, calcium, chloride, creatinine
- Albumin, alkaline phosphatase, total bilirubin, total protein, SGOT [AST], SGPT [ALT]
- FISH panel will use probes to detect for abnormalities in chromosomes 13q, 12, 11q, and 17p.
- For CLL patients only.
- Pregnancy tests for females of childbearing potential. A female of childbearing potential (FCBP) is a sexually mature female who: 1) has not undergone a hysterectomy or bilateral oophorectomy; or 2) has not been naturally postmenopausal (amenorrhea following cancer therapy does not rule out childbearing potential) for at least 24 consecutive months (i.e., has had menses at any time in the preceding 24 consecutive months). Female of childbearing potential must have a negative serum β -Hcg pregnancy

test result within 3 days of first study dose.

- k. For cycles 7 and higher, patient will be required to return for evaluation and to receive KPT-330 every 3rd month (eg. Cycle 7 Day 1, Cycle 10 Day 1, Cycle 13 Day 1....)

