- a. Initial medical history should include: baseline symptoms; a detailed history of prior cancer therapies including start and stop dates, disease progression during or after therapy, as well as discontinuations due to intolerability or any other serious illness; family and social history; calculation of Rai Stage (for CLL patients)
- b. Progress notes should include: new symptoms or adverse events, ECOG performance status (Appendix A), documentation of physical exam, status of disease.
- c. Ophthalmologic exam: required at screening and if clinically indicated during study. Prior to dilation: best corrected visual acuity, visual field examination via automated perimetry, tonometry, and color vision test. Dilated funduscopy and slit lamp exam including anterior segment photos to document lens clarity.
- d. For ECOG performance status, see Appendix A
- e. Prothrombin time, international normalization ratio, and activated partial thromboplastin time
- f. Sodium, potassium, bicarbonate, BUN, calcium, chloride, creatinine
- g. Albumin, alkaline phosphatase, total bilirubin, total protein, SGOT [AST], SGPT [ALT]
- h. Only if not done prior to initiation of ibrutinib
- i. Pregnancy tests for females of childbearing potential. A female of childbearing potential (FCBP) is a sexually mature female who: 1) has not undergone a hysterectomy or bilateral oophorectomy; or 2) has not been naturally postmenopausal (amenorrhea following cancer therapy does not rule out childbearing potential) for at least 24 consecutive months (i.e., has had menses at any time in the preceding 24 consecutive months). Female of childbearing potential must have a negative serum β -

Hcg pregnancy test result within 3 days of first study dose.

- j. Reassessment off therapy will occur 4-6 weeks from the last dose of study therapy. For patients removed from study for reasons other than disease progression, reassessment will then occur then every 6 months until progression or an alternative therapy is started.
- k. Restaging scans and immunophenotyping will be performed every 3 cycles for the first year and then every 6 months thereafter.

Bilateral bone marrow biopsies are preferred for lymphoma patients.

- l. A bone marrow biopsy and aspirate should be performed to confirm a complete response if there was bone marrow involvement at diagnosis, clinical MRD flow should be performed in this case.

	1															2	Q3 Cycles	Relapse
Day	1							2	8	15						16	1	1

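### The pregnancy-test waiver in 3.1.7 and the contraception rule in 3.1.6 are looser than calendar footnotes j and i and Section 5.5, and nothing says which wording prevails

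*Combined protocol and SAP*

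**What the plan says.** **Pregnancy test.** Section 3.1.7 requires a negative serum test within 3 days of first dose in women of childbearing potential, a term it does not define. It then permits a waiver for two groups: women who are surgically sterilized by any means, and women "who are > 45 years old and have not experienced menses for > 2 years". Neither group carries a condition on the cause of amenorrhea.

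Section 10 defines childbearing potential in footnote j (escalation and expansion calendar) and footnote i (Cohort 3 calendar), in the same terms: a sexually mature woman who "has not undergone a hysterectomy or bilateral oophorectomy; or 2) has not been naturally postmenopausal" for at least 24 consecutive months. Both footnotes add that "amenorrhea following cancer therapy does not rule out childbearing potential". Both then paraphrase the second limb as a woman who "has had menses at any time in the preceding 24 consecutive months", which takes no account of cause.

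**Contraception.** Under 3.1.6, women able to reproduce and men with such partners "must agree to use an effective contraceptive method during the course of the study". Under 5.5, the rule for women of childbearing potential is that they "must agree to use dual methods of contraception and have a negative serum pregnancy test at screening". For men with a partner who could conceive, 5.5 asks for a barrier method. Both sections then give the same list of acceptable methods, which includes single non-barrier methods.

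**Registration.** Section 4 states: "Patients will be registered after meeting all entry requirements, clearance by the Protocol Coordinator". Subsites must also submit a signed eligibility checklist, source documents for every inclusion and exclusion criterion, and copies of the baseline tests that the calendar requires.

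**The concern.** Section 3.2.11 excludes pregnant women because it is not known whether selinexor is teratogenic or abortifacient. The test and the contraception rule put that exclusion into practice. Section 3 is the text that sites turn into a checklist, and on both matters it is the looser one.

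The waiver reaches the group that the footnotes single out for caution. Cohorts 1 and 2 require at least one prior therapy for CLL or NHL (3.1.1), so amenorrhea after cancer treatment is a realistic case there. A site relying on 3.1.7 could omit a test that the calendar demands and reasonably believe that it had complied.

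**Working it through.** The protocol gives no figure to reproduce here. The check applies each rule to the same patient, reading the footnotes in their evident sense (either operation, or natural postmenopause, ends childbearing potential).

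| Patient | Section 3 | Footnotes j/i or 5.5 | Agree? |
|---|---|---|---|
| Woman aged 47, three years without menses after chemotherapy | 3.1.7: test may be waived | Footnotes: not naturally postmenopausal, so tested | No |
| Woman with tubal sterilization, still menstruating | 3.1.7: test may be waived | Footnotes: neither listed operation, so tested | No |
| Woman over 45, naturally postmenopausal for more than 24 months | 3.1.7: test may be waived | Footnotes: not of childbearing potential | Yes |
| Woman of childbearing potential using only an oral contraceptive | 3.1.6: meets the criterion | 5.5: second method needed | No |
| Man whose partner is of childbearing potential and uses an intrauterine device | 3.1.6: meets the criterion | 5.5: barrier method needed | No |

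In the first row, the footnotes' own paraphrase ("has had menses at any time in the preceding 24 consecutive months"), read alone, would release the woman, because she has had no menses for 24 months. That contradicts both the requirement of natural postmenopause and the parenthetical on cancer therapy, so the footnotes need a small repair too.

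**Size of the therapy-related amenorrhea group.** Women affected = N × share who are women × share of those women over 45 with more than 2 years of therapy-related, not natural, amenorrhea.

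- N is from Section 13.2 for Cohorts 1 and 2: 32 expected, 50 at most.
- Both shares are assumptions, since the protocol gives neither: 30–50% women, and 0–10% of those with qualifying amenorrhea.
- N = 32: low 32 × 0.30 × 0 = 0; high 32 × 0.50 × 0.10 = 1.6.
- N = 50: low 50 × 0.30 × 0 = 0; high 50 × 0.50 × 0.10 = 2.5.

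This counts women whose test could be waived, not pregnancies missed. It leaves out women sterilized by other operations, for whom there is no figure. The amenorrhea question matters less in the 10 patients of Cohort 3, whose ibrutinib is their initial CLL/SLL therapy. The sterilization and contraception mismatches apply in all cohorts.

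**The case against.** The best defence is that the rules are cumulative. The waiver is permissive, so testing everyone whom the footnotes cover complies with every section, and anyone who meets 5.5 also meets 3.1.6. Pregnancy is excluded separately, registration needs central clearance, and subsites must send calendar-required tests.

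Most of this stands, and it keeps the point small. It does not remove it. An express waiver competes with the footnotes rather than adding to them, and whether the calendar requires a test depends on the definition in dispute. Registration papers are also not a complete check on timing: treatment should start within 7 business days of registration, while the test must fall within 3 days of first dose, so the test that counts can come after the submission.

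A reader might infer more than the text supports:

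- *The footnotes make almost every woman of childbearing potential, because they join two negatives with an or.* That is the literal parse, but it leads only to more testing. It is not a safety gap.
- *Section 5.5 overrides the waiver because it contains none.* Section 5.5 covers only women of childbearing potential, so it needs no waiver for others and does not settle who they are.
- *The footnotes also need the age-45 floor.* On their evident reading, a woman of 45 or younger who is naturally postmenopausal for 24 months is not of childbearing potential. A floor would make her so and bring her under the dual-method rule. The conflict does not call for that.
- *Pregnant women are likely to be dosed.* Nothing in the documents gives a basis for any missed pregnancy in women over 45 with more than two years without menses.

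It is also fair to say that 5.5 is loose in itself. Having required dual or barrier methods, it lists single non-barrier methods as acceptable, so copying it unchanged into 3.1.6 would carry that ambiguity over.

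**Conclusion.** The conflict holds as a minor inconsistency in patient-safety wording. Section 3.1.7 allows a waiver that footnotes j and i do not, for therapy-related amenorrhea and for sterilization other than hysterectomy or bilateral oophorectomy. Section 3.1.6 asks for less than 5.5: one method against two for women, and no barrier requirement for men. No section states which text prevails.

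These textual findings need no assumption. The size does: at most about 1.6 women at 32 patients or 2.5 at 50 under the assumed shares for therapy-related amenorrhea, and possibly none. DLT assessment, dose finding, the Cohort 3 decision rule and the other analyses are unaffected.

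**What to change.** 1. **Section 3.1.7.** Limit the waiver to women who have had a hysterectomy or bilateral oophorectomy, or who are over 45 and naturally postmenopausal for at least 24 consecutive months. State that amenorrhea following cancer therapy does not qualify.
2. **Sections 3.1.6 and 5.5.** Make 3.1.6 require what 5.5 requires: dual methods for women of childbearing potential, and an effective barrier method for men sexually active with a woman of childbearing potential. State in both sections that the list of acceptable methods does not replace those requirements.
3. **Footnotes j and i.** Delete the paraphrase about menses in the preceding 24 months and keep the rest. No age floor is needed there.

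The cost is amendment wording, an updated eligibility checklist, and a few serum tests at sites that now use the waiver. Sites that already follow the calendar and 5.5 should see little change.

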3.2 Exclusion Criteria

- 3.2.1 Patients who are concurrently receiving any other investigational agents.
- 3.2.2 Patients who have received:
- Radiation or chemotherapy \leq 4 weeks,
 - Mitomycin C, nitrosureas, or radio-immunotherapy \leq 6 weeks, or
 - Immunotherapy or targeted therapy (such as kinase inhibitors) \leq 2 weeks prior to cycle 1 day 1. Patients who are on ibrutinib at study entry are not required to discontinue ibrutinib for any period of time.
- Palliative steroids for disease related symptoms are allowed as long as dose is tapered down to an equivalent of \leq 10mg of oral prednisone daily on cycle 1 day 1.
- 3.2.3 Patients who have underwent autologous or allogeneic stem cell transplant \leq 4 weeks prior to cycle 1 day 1 or have active graft-versus-host disease are excluded.

- 3.2.4 Patients unable to swallow tablets or capsules, those with uncontrolled vomiting or diarrhea or disease significantly affecting gastrointestinal function and/or inhibiting small intestine absorption such as; malabsorption syndrome, resection of the small bowel, or poorly controlled inflammatory bowel disease affecting the small intestine
- 3.2.5 Patients who are 20% below their ideal body weight (BMI calculator can be found at http://www.cdc.gov/healthyweight/assessing/bmi/adult_bmi/english_bmi_calculator/bmi_calculator.html)
- 3.2.6 Patients must not be receiving systemic anticoagulation with warfarin. Patients must be off warfarin for 30 days prior to enrollment. Patients who require anticoagulation with an agent other than warfarin will not be excluded, but must be reviewed by the principal investigator prior to enrollment.
- 3.2.7 As ibrutinib is extensively metabolized by CYP3A4/5, and patients must not require continued therapy with a strong inhibitor or inducer of CYP3A4/5. See Appendix B for a list of these medications.
- 3.2.8 Patients with active HIV or Hepatitis C. (HIV-positive patients on combination antiretroviral therapy or Hepatitis C-positive patients on antiviral therapy are ineligible because of the potential for pharmacokinetic interactions with ibrutinib or selinexor. In addition, HIV patients are at increased risk of lethal infections when treated with potentially marrow-suppressive therapy.)
- 3.2.9 Patients with secondary malignancy that requires active systemic therapy that will interfere with interpretation of efficacy or toxicity of selinexor. (Note: Patients with basal or squamous skin carcinoma, cervical carcinoma in situ, localized breast cancer requiring hormonal therapy or localized prostate cancer (Gleason score <5 are allowed).
- 3.2.10 Patients with active known central nervous system (CNS) involvement of CLL or lymphoma. (Patients with history of CNS CLL or lymphoma now in remission are eligible for the trial.)
- 3.2.11 Patients who are pregnant or breast feeding. (Pregnant women are excluded from this study because it is unknown if selinexor has teratogenic or abortifacient effects. Because there is an unknown but potential risk for adverse events in nursing infants secondary to treatment of the mother with selinexor, breastfeeding should be discontinued if the mother is treated with selinexor.)
- 3.2.12 Patients must have recovered all toxicities from prior therapy or radiation to grade 1 or less (excluding alopecia).

- 3.2.13 Patients may not have had major surgery within 10 days of enrollment, or minor surgery within 7 days of enrollment. Examples of minor surgery include dental surgery, insertion of a venous access device, skin biopsy, or aspiration of a joint. The decision about whether a surgery is major or minor can be made at the discretion of the treating physician.
- 3.2.14 Patients with uncontrolled intercurrent illness including, but not limited to, ongoing or active infection, symptomatic congestive heart failure, unstable angina pectoris, cardiac arrhythmia, or psychiatric illness/social situations that would limit compliance with study requirements.
- 3.2.15 Patients enrolling in Cohort 3 must not have ongoing Grade 3 or higher toxicity due to ibrutinib at study entry (except hypertension that is medically managed).

3.3 Inclusion of Women and Minorities

Both men and women of all races and ethnic groups are eligible for this trial.

4. REGISTRATION PROCEDURES

For subsite patients, sites must send the signed consent form, documentation of the consent process, and the Screening Form (refer to Supplemental Forms Document) within 2 business days of initial consent.

Patients will be registered after meeting all entry requirements, clearance by the Protocol Coordinator, and signing of the informed consent.

OSU patients will be registered by the OSU research coordinator, as per their standard practice.

Subsite patients will have eligibility verified and will be entered on study centrally at the Ohio State University by the Multi-Center Trial Program (MCTP). All subsites must email the MCTP to verify slot availability prior to consenting patients. The required forms, including Eligibility Criteria Checklist and Registration Form, can be found in the Supplemental Forms Document.

To register a subsite patient, the following documents must be completed by the subsite research team and faxed or securely e-mailed to the MCTP:

- Copy of all baseline tests required per the protocol calendar. Tests must be within the specified window.
- Signed Patient Consent Form
- Signed Patient HIPAA Authorization Form
- Consent Documentation Note

- Completed & Signed Eligibility Checklist (refer to Supplemental Forms Document)
- Registration Form (refer to Supplemental Forms Document)
- Source documents verifying every inclusion & exclusion criteria
 - Note: every inclusion and exclusion criteria must be documented in the patient's medical record (emails or other notes outside the medical record will not be considered source documentation)

Upon receipt of registration documents, the MCTP will send an email confirmation of receipt. If confirmation of receipt is not received within 1 hour of submission, please call or page the MCTP.

Upon receipt of all required registration documents and upon verification the subsite patient meets all eligibility criteria, the MCTP will:

- Register the patient on the study
- Fax and/or e-mail to the subsite the completed Registration Form with the assigned study ID as confirmation of patient registration

Following registration, patients should begin protocol treatment within 7 business days. Issues that would cause treatment delays should be discussed with the Principal Investigator and MCTP as soon as possible. If a patient does not receive protocol therapy following registration, the patient's registration on the study may be canceled, after discussion with the PI and MCTP.

Each participating institution will order study agents directly. Agents may be ordered by a participating site only after the initial IRB approval for the site has been forwarded to the MCTP.

